- ⁴ Visit only conducted for subjects that don't enroll in the phase 4 continuation study or transition immediately to commercial pexidartinib. For patients who miss the 30-day or 12-week post-treatment follow-up MRI, post-treatment radiographic assessments from any source (e.g., primary care provider) within 24 weeks of the last dose are acceptable.
- ⁵ If there is a Grade 2 or higher ALT or AST elevation (i.e., $>3 \times$ ULN) at any time during treatment, the patient should be followed closely (see [Section 14.7](#) for monitoring details).
- ⁶ On C1D1, obtain predose. On C1D15, obtain predose (AM) and 1, 2, 4 and 6 hours postdose. During continued dosing, obtain once every 4 weeks (predose). For patients with afternoon clinic visits, see [Section 20.1](#).
- ⁷ For women of child-bearing potential.
- ⁸ Patients enrolled after the implementation of Amendment 8 will complete these two patient reported outcome (PRO) instruments predose at the clinic on C1D1, C1D15, C2D1, and monthly thereafter, and every 12 weeks after C40, while continuing study drug administration, and at the End of Study visit.
- ⁹ For patients enrolled after the implementation of Amendment 8, six (6) questionnaires will be dispensed at the indicated clinic visits with instructions and reminders to complete the questionnaire on an outpatient basis for 6 consecutive days (Day -6 to Day -1) prior to each monthly clinic visit on C1D1, C2D1, C3D1, etc. (or at every 12- or 24-week visit after C40) while continuing study drug administration. The patient should return the completed questionnaires to site staff at each of the subsequent monthly clinic visits on C1D1, C2D1, C3D1, etc.
- ¹⁰ Morning urine NTX and CTX-II and the following serum markers: IL-6, CSF-1. CD14+/CD16+ monocytes predose (AM) on C1D1 only.
- ¹¹ This assessment will occur every 8 weeks during continued dosing, and every 24 weeks after C40, and (for subjects that don't enroll in the phase 4 continuation study or transition to commercial pexidartinib) approximately 30 days and 12 weeks after the last dose of study drug; additional detail regarding MRI is included in footnote 2. For PVNS patients, the Sponsor will receive radiologic images for possible retrospective analysis of treatment response, to be performed by a central vendor.
- ¹² Monitored throughout the study via safety assessments, observation, and participant reporting.

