10.0 SELECTION OF STUDY POPULATION

All patients must participate in the consent process. During the consent process, the person obtaining consent must inform the patient of all elements of informed consent. No protocol-specific procedures, including screening procedures, are to be performed until the patient has signed and dated an institutional review board (IRB)/independent ethics committee (IEC)-

approved informed consent form. The study begins with the signing and dating of the informed consent form. Patients must also meet the inclusion and exclusion criteria to be enrolled in the study.

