5. All associated toxicity from previous or concurrent cancer therapy must be resolved (to \leq Grade 1 or Baseline) prior to administration of pexidartinib.

6. Willing and able to provide written informed consent prior to any study related procedures and to comply with all study requirements.
7. ECOG performance status 0 or 1.
8. Life expectancy ≥ 3 months.
9. Adequate hematologic, hepatic, and renal function (absolute neutrophil count $\geq 1.5 \times 10^9/L$, Hgb >9 g/dL, platelet count $\geq 100 \times 10^9/L$, AST/ALT $\leq 2.5 \times$ ULN or $<5 \times$ ULN in the presence of liver metastases, albumin ≥ 3 g/dL, creatinine $\leq 1.5 \times$ ULN or calculated CrCl >60 mL/min using Cockcroft-Gault formula).

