24.0 STATISTICAL ANALYSIS

24.1 Safety Analysis

All patients in all cohorts who received study medication will be considered evaluable for safety regardless of their duration of treatment.

The objective of the dose escalation is to determine a dose of pexidartinib for which the rate of DLTs is less than 33%. Safety variables to be analyzed are AEs, laboratory test results (hematology, clinical chemistry, coagulation parameters, and urinalysis), ECG, and vital signs. Adverse event terms recorded on the CRFs will be mapped to preferred terms using the Medical Dictionary for Drug Regulatory Activities (MedDRA®) version 7.1 or higher. All AEs will be summarized for each dose group according to the system organ class and preferred term within the organ class. Adverse events will be tallied for overall frequency (number and percentage of subjects), worst reported severity, and relationship to study drug for each preferred term per subject. Serious adverse events will be similarly summarized. Listings of deaths, SAEs, and AEs leading to early termination of study treatment or premature withdrawal from study will also be provided. In addition, all events meeting the criteria of a DLT will be tabulated as a separate listing by subject and dose group. Laboratory variables will be examined using mean change in value from baseline to scheduled time points for each pexidartinib dose group. Laboratory values

will also be categorized according to their CTCAE (version 4) toxicity grade and tabulated by worst on-study toxicity grade and pexidartinib dose group. The baseline value of a variable is defined as the last value obtained on or before the date and time of the first pexidartinib dose. Concomitant medications will also be summarized.

ECG/QT Analysis:

All ECG information will be listed by patient, including change from baseline for numeric ECG parameters (based on means of the triplicate assessments). Summaries by time-point will be provided for absolute and change from baseline numeric ECG parameters (including categorical summaries for QTc absolute and change from baseline). Plots of mean ECG data and their change from baseline over time will be provided. For each of the time points, the available triplicate QTc values will be averaged for all analyses.

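### The laboratory grade table in Section 24.1 has no baseline grade, so an unchanged entry abnormality is tabulated as on-study toxicity of the dose group

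*Combined protocol and SAP*

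**What the plan says.** Section 24.1 plans two laboratory summaries.

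- **Group means:** "Laboratory variables will be examined using mean change in value from baseline to scheduled time points for each pexidartinib dose group".
- **CTCAE version 4 grades:** these are "tabulated by worst on-study toxicity grade and pexidartinib dose group".

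The same section supplies a usable baseline: "The baseline value of a variable is defined as the last value obtained on or before the date and time of the first pexidartinib dose". It does not apply that baseline to the grades. It asks for no baseline grade, no shift and no requirement that a grade worsen, and no other section adds one. Section 24.5 says only that analyses are in general descriptive. The term on-study is not defined.

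Two other places determine what can enter the grade table.

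- **Section 10.1, criterion 9:** AST/ALT may be up to 2.5 x ULN, or below 5 x "ULN in the presence of liver metastases".
- **Extension cohort flow chart, footnote 5:** the text beginning "If there is a Grade 2 or higher ALT or AST elevation" equates that grade with values above 3 x ULN. Attachment 1 repeats the threshold.

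**The concern.** A worst-grade table by dose group is normally read as what happened on the drug at that dose. Here the eligibility limit and the protocol's own grade threshold overlap. A patient with liver metastases can be eligible and already Grade 2, so the table can report as on-study toxicity something that was present before the first capsule and did not change.

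Safety is a primary objective of the dose escalation phase (Section 8.1), and Section 24.1 plans no other table of laboratory grades by dose group. Escalation groups hold 3 to 6 patients, so one such patient can make two dose levels look different. For QTc, Section 24.1 asks for categorical summaries of both the absolute value and the change from baseline. Laboratory grades get the absolute category only.

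**Working it through.** The plan states no figure on this point, so there is none to reproduce. The main check compares the texts. Two calculations then give a sense of scale.

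**1. The overlap, from the documents' own numbers**

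- Highest AST/ALT allowed at entry with liver metastases: below 5 x ULN (Section 10.1, criterion 9).
- Protocol threshold for Grade 2: above 3 x ULN (extension flow chart footnote 5; Attachment 1).
- A patient above 3 and below 5 x ULN is therefore both eligible and already at least Grade 2. If the value stays there, the worst on-study grade is Grade 2.
- Without liver metastases the entry limit is 2.5 x ULN, which is below 3 x ULN. The AST/ALT route is closed to those patients at entry.
- Criterion 9 sets no lymphocyte limit, and Section 16.4 describes lymphopenia as common in patients with advanced solid tumors. Grade cut-points for lymphocytes are not in the documents, so this is not quantified.

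**2. Small dose groups**

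Let q be the share of patients already at the grade at entry. The documents do not give q, so a range is assumed. The chance of at least one such patient among n is 1 − (1 − q)^n.

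| q (assumed) | n = 3 | n = 6 |
|---|---|---|
| 0.05 | 14% | 27% |
| 0.10 | 27% | 47% |
| 0.20 | 49% | 74% |
| 0.30 | 66% | 88% |

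One such patient is 1/3 = 33% of a group of 3, or 1/6 = 17% of a group of 6.

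**3. Illustration for patients with liver metastases, no drug effect**

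Assumptions, none of them from the documents unless stated:

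- The true AST or ALT level is log-uniform between 0.5 and 5 x ULN.
- Each measurement is the true level times lognormal noise with within-patient CV 20%, that is log-SD = √ln(1 + 0.20²) = 0.198.
- The screening value must be below 5 x ULN (criterion 9). It serves as baseline, because the flow charts schedule chemistry at screening and not on Cycle 1 Day 1.
- There are three on-treatment tests. In the escalation chart that corresponds to C1D8, C1D15 and C2D1.
- Grade boundaries are 3 x ULN (protocol) and 5 x ULN (assumed, as the documents do not state the next cut).

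Plausibility check: the share of true levels above 3 x ULN is ln(5/3)/ln(10) = 0.511/2.303 = 22%. The entry limit removes some of the highest, and about 19% of admitted patients exceed 3 x ULN at screening.

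| Within-patient CV | Worst value above 3 x ULN, current wording | Same, counted only if the grade worsens from baseline |
|---|---|---|
| 15% | 26% | 11% |
| 20% | 27% | about 15% |
| 30% | 30% | 20% |

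At CV 20% the difference, 27 − 15 = about 12 percentage points, is entry abnormality that did not worsen. The remaining 15% is noise across a cut-point.

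These rates apply only to patients with liver metastases. If they form a share m of a dose group, they contribute 0.27 × m to the group's rate: 2.7% for m = 0.10 and 13.5% for m = 0.50. The documents do not give m.

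**The case against.** The strongest reply is that nothing turns on this table. Escalation follows DLTs (Section 16.4), which Section 24.1 lists separately by subject and dose group. Liver management follows Tables 3 and 4. Clinically significant laboratory abnormalities are recorded as adverse events under wording in Section 26.1 that already requires them to be treatment-emergent, and those events are then summarized by dose group, severity and relationship to drug. All of that stands. A reader might infer that the missing baseline grade distorts dose decisions or the AE tables. The documents do not support that.

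A reader might also infer that the pre-dose screening value itself counts as on-study, because Section 10.0 says: "The study begins with the signing and dating of the informed consent form". That reading is strained. The sentence concerns consent, Section 24.1 defines baseline separately, and Section 24.2 contrasts effusion procedures before study entry with those on study. What stands is that the term is undefined and one line would settle it.

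Third, the AST/ALT route is narrow. It needs liver metastases, and because all extension cohorts start at the same 1000 mg/day, a spurious difference between doses concerns mainly the escalation groups. This stands too and limits the size.

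The mean-change summary does not answer the point, because a group mean cannot show whose grade worsened. Nor does the AE wording: it governs which results become adverse events, not what goes into the grade table. It is fair to say that worst absolute grade has its own use, so the table should be supplemented and not removed.

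**Conclusion.** The point holds as a defect in one descriptive safety table. The overlap between the 5 x ULN entry limit and the 3 x ULN Grade 2 threshold follows from the protocol's own figures and needs no assumption. An unchanged entry abnormality is tabulated as on-study toxicity of the dose group, and no other section corrects that table. No sample size, power or DLT figure changes.

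The size is illustrative. The 27% and 15% depend on an assumed distribution of entry values, CV and number of tests, and on an assumed 5 x ULN cut, and they apply only to patients with liver metastases. A baseline-referenced count roughly halves the apparent rate under those inputs. It does not bring it to zero, because values near a cut-point still cross it by chance. Under the same model, a patient stable at 4 x ULN is still flagged as worsened in about 40% of cases.

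**What to change.** In Section 24.1:

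1. Keep the worst-grade table.
2. Add, by dose group, a shift table of baseline grade against worst grade after the first dose, using the baseline already defined there.
3. Flag a laboratory grade as treatment-emergent only if it is worse than the baseline grade.
4. Define on-study for these tables as after the first pexidartinib dose.

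The cost is a few lines of text and one additional programmed table. It needs no new data and adds no patient or site burden. The table's footnote should say that a one-grade shift near a cut-point may be measurement noise.

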6.4.4 Safety Pharmacology

In GLP-compliant respiratory and central nervous system safety studies, the NOEL for pexidartinib was 200 mg/kg in rats. Additionally, three GLP-compliant safety pharmacology studies addressed the potential adverse cardiovascular or cardiac electrophysiological effects of pexidartinib. When evaluated in a serum free hERG study, pexidartinib was shown to bind to the channel (IC₅₀ 0.7 µM). However, in a follow-up cardiac Purkinje fiber study, no test article-related effects on repolarization, AP amplitude or speed of cardiac depolarization were observed. Furthermore, in a dog in vivo GLP cardiovascular safety study, all electrocardiographic parameters were qualitatively and quantitatively within normal limits, demonstrating that pexidartinib does not prolong cardiac repolarization up to the highest dose tested (1000 mg/kg).

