13.2 Run-In Period (Selected Cohorts) – Cycle 1 Day(-7), Day(-6), and Day(-4)

1. All 3 days: Recording of concomitant medications and adverse events.

2. All 3 days: Vital signs (sitting blood pressure, pulse rate, and respiratory rate and oral temperature [°F]).
3. All 3 days: Pre-dose blood sample collection for PK analysis and response biomarkers.
4. C1D(-7): Post-dosing blood collection for PK analysis.

13.3 Pre-Treatment (Baseline): Cycle 1 Day 1

Patients will return to the clinic on C1D1 and will undergo the following procedures:

1. Recording of concomitant medications.
2. Vital signs (sitting blood pressure, pulse rate, and respiratory rate and oral temperature [°F]).
3. Standard 12-lead ECG in triplicate 2 minutes apart.
4. Pre-dose blood sample collection for PK analysis and response biomarkers.
5. Pre-dose morning urine collection for response biomarkers.

13.4 Post-Treatment: Cycle 1 Day 1 and Cycle 1 and Day 2

On C1D1, each patient will receive the assigned dose of test article. AE monitoring will be continuous. Vital signs, ECGs, laboratory evaluations, and PK sample collections will be completed at designated times during the study (see [Trial Flow Charts](#)). The blood sample for PK analysis should be collected at the scheduled time, within the windows noted in the PK section. ECG in triplicate will be repeated at 2, 4, and 6 hours after administration of study drug. Pulse and blood pressure will be repeated at 1 and 4 hours post administration of study drug on C1D1. Patients will return to the clinic on the morning of C1D2 prior to dosing on that day for evaluation and blood draw to obtain the predose PK time-point (approximately 12 hours after the previous evening dose for a BID dosing regimen).

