20.0 PHARMACOKINETIC EVALUATION

20.1 Blood Collection

Venous blood samples will be collected in lithium heparin to measure concentrations of pexidartinib for each PK blood collection.

For QD dosing in the dose escalation cohorts, PK samples will be obtained on C1D1 and C1D15 within 30 minutes before dose administration (predose, time 0) and at 30 minutes, 1, 2, 4, and 8 hours post-dosing. For BID dosing, PK samples will be obtained on C1D1 and C1D15 predose (AM) and 1, 2, 4, and 7 hours postdose. The second dose will be administered, and a PK sample will be obtained 1 hour post the second dose (8 hours post the first dose). Predose samples will be obtained on C1D2, C1D8, and C1D16, and then every 4 weeks during continued dosing. Patients should be informed to refrain from taking study drug until they arrive in the clinic. If a patient experiences a DLT or SAE, a single blood sample for PK analysis should be obtained within 48 hours of the event. Samples will be collected and processed according to the instructions in [Attachment 2](#) and [Attachment 3](#).

In the Extension cohorts, PK samples should be obtained pre-dose on C1D1. On C1D15, the samples should be obtained pre-dose and 1, 2, 4, and 6 hours postdose. During continued dosing, PK samples should be obtained once every 4 weeks (predose). PK sampling will no longer occur beyond C40.

Blood samples for PK analysis should be collected at the requested time but the following sample collection windows will be allowed: ± 5 minutes for the 30-minute postdose sample; ± 10 minutes for the hour 1 through 4–8 postdose samples; within ± 30 minutes of dosing on C1D2, C1D8, and C1D16. The exact time of collection should be noted in the CRFs.

If a patient has an afternoon clinic visit, the patient should be instructed to take his or her AM and PM dose as usual. When the patient arrives at the clinic, the PK blood sample should be obtained even though it will be drawn after the patient's AM dose. The time of the AM dose should be entered on the PK CRF, and a comment should be added to the comment field of the CRF to indicate that the PK sample was collected after the AM dose.

Biological specimen samples for pharmacokinetic analysis must be identified with labels provided by the Sponsor.

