The primary study variable for the QT evaluation will be the study specifically corrected QT interval (QTcS or QTcF or QTcB) change from baseline. The correction formulae for QTc will be estimated based on linear or non-linear regression of predose QT interval data and RR data.

In addition, change from baseline for other ECG variables (QT, RR, heart rate, PR, QRS) will be summarized.

Corrected mean changes from baseline in QTc together with one-sided upper 95% confidence intervals will be derived for each timepoint to interpret the effect of pexidartinib on the QT interval.

The following criteria on baseline measurements will be considered in the analysis of the QT interval. Patients who fall within these criteria may bias the interpretation of pexidartinib effect on QT interval. Data from these patients may be analyzed separately from the general patient population.

- Heart rate (HR) greater than 90 or less than 45 beats per minute
- Sustained systolic blood pressure measurements <90 or >140 mmHg or diastolic blood pressure measurements <50 or >90 mmHg at screening or Day -1
- Any concomitant medications that prolong QT/QTcF interval
- History and/or family history of congenital long QT syndrome or sudden death
- Clinically significant abnormal ECG (e.g., marked QT/QTcF prolongation)
- More than 30 msec difference in two extreme, highest and lowest reads of any baseline QTcF at a specific time point
- Short QTcF (<300 msec) at screening or baseline
- Screening or baseline ECG evidence of atrial fibrillation, atrial flutter, complete right or left bundle branch block, WPW-syndrome, or cardiac pacemaker

- QRS and/or T-wave judged to be unfavorable for a consistently accurate QT measurement at baseline (e.g., indistinct QRS onset, low amplitude T-wave, merged T- and U-waves, prominent U-waves)

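### The QT analysis has no dose or concentration term and leaves the correction formula open, so the timed-ECG estimate at 1000 mg/day is either diluted by pooling or rests on a handful of patients

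*Combined protocol and SAP*

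**What the plan says.** The QT plan is in Section 24.1, under ECG/QT Analysis.

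- **Variable.** "The primary study variable for the QT evaluation will be the study specifically corrected QT interval (QTcS or QTcF or QTcB) change from baseline". No rule is given for choosing among the three. The sentence that follows has the correction estimated by regressing predose QT on RR, which describes a study-specific formula rather than a fixed one. Section 10.2 already defines the ECG exclusion in terms of QTcF.
- **Estimator.** "Corrected mean changes from baseline in QTc together with one-sided upper 95% confidence intervals will be derived for each timepoint to interpret the effect". The supporting tables have the same layout: "Summaries by time-point will be provided for absolute and change from baseline numeric ECG parameters".
- **Contrast within the section.** Laboratory data are stratified by dose: "Laboratory variables will be examined using mean change in value from baseline to scheduled time points for each pexidartinib dose group". Adverse events are also summarised by dose group. The QT text has no such clause.
- **ECG data.** Section 18.3 limits triplicate ECGs to dose escalation. Section 13.4 sets the Cycle 1 Day 1 times: "ECG in triplicate will be repeated at 2, 4, and 6 hours after administration of study drug". Section 13.6 repeats those hours on Day 15. Extension patients have ECGs at screening, Day 15 and End of Study (extension flow chart), and Section 14.4 gives no post-dose hour for the Day 15 recording.
- **PK data.** For twice-daily dosing in escalation, Section 20.1 states: "PK samples will be obtained on C1D1 and C1D15 predose (AM) and 1, 2, 4, and 7 hours postdose". The once-daily schedule also includes 2 h and 4 h.

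**The concern.** A mean per time point answers a clear question only when everyone contributing to it receives a similar dose. Escalation starts at 200 mg once daily and the recommended dose is 1000 mg/day. Read literally, the plan puts all escalation doses into one mean at each time. If the QTc effect grows with dose, that mean understates the effect at 1000 mg/day whenever most contributing patients took less. If the tables are split by dose instead, each cell holds very few patients and the upper bound carries little information.

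The open choice of correction adds a second weakness. Three candidate primary variables can give three different bounds, and nothing in the text fixes which one counts.

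At stake is how well the trial characterises QTc at the dose carried into the extension cohorts. Much of the information needed is collected already: ECG and PK times coincide at 2 h and 4 h on both intensive sampling days. The plan relates exposure to antitumour activity (Section 24.2) and to SAEs (Section 24.3), but not to QTc.

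**Working it through.** **Inputs from the document.** 3 to 6 patients per escalation level (Section 24.6); up to 50 escalation patients and about 70 extension patients (Section 9.2); extension dose 1000 mg/day (Section 9.1); starting dose 200 mg once daily (Section 7.1). No QT margin, SD or precision target is stated, so there is no QT figure of the plan's own to reproduce.

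**Assumptions.** The SD of QTc change is not given; 10, 15 and 20 msec are used. The escalation levels are not listed; four grids are used (mg/day):
- A: 200, 400, 600, 1000, equal numbers
- B: 200, 300, 400, 600, 900, 1000, equal numbers
- C: grid B plus 1200, equal numbers
- D: grid A with half of the patients at 1000

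**Step 1: splitting by dose.** Distance from mean to one-sided upper 95% bound = t(0.95, n-1) x SD / sqrt(n).
- n = 3: 2.920 / 1.732 = 1.69 SD, or 16.9, 25.3 and 33.7 msec at SD 10, 15 and 20.
- n = 6: 2.015 / 2.449 = 0.82 SD, or 8.2, 12.3 and 16.5 msec.

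**Step 2: pooling escalation doses.** Under a dose-proportional effect, the fraction retained is mean dose / 1000.
- A: 2200/4 = 550, 55%
- B: 3400/6 = 567, 57%
- C: 4600/7 = 657, 66%
- D: 4200/6 = 700, 70%

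An illustrative true effect of 20 msec at 1000 mg/day would therefore read as 11-14 msec. With 50 patients pooled, the bound lies 0.24 SD above that mean (2.4 msec at SD 10, before adding the spread between doses). It would be tight around the wrong quantity.

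**Step 3: adding the extension ECGs.** Suppose the 70 extension patients were pooled in at Day 15.
- With 50 escalation patients, grid A: (50 x 550 + 70 x 1000)/120 = 812, 81%. Grid D gives 88%.
- With 24 escalation patients, the range is 89% (A) to 92% (D).

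The extension patients alone, all at 1000 mg/day, give a bound 0.20 SD above the mean (2.0, 3.0 and 4.0 msec at the three SDs). Those SDs are carried over from the triplicate case. A single ECG at an unstated hour, set against a screening baseline, would probably vary more.

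**Step 4: what a dose term would buy.** Fit change = a + b x dose, one observation per patient, and predict at 1000 mg/day. The distance to the bound is t(0.95, N-2) x SD x sqrt(1/N + (1000 - mean dose)^2 / Sxx), where Sxx is the sum of squared dose deviations over all patients.
- Grid A, N = 24 (6 per level): Sxx = 6 x 350,000 = 2,100,000; 1.717 x sqrt(1/24 + 450^2/2,100,000) = 0.64 SD, against 0.82 SD for the by-dose mean of the same 6 patients.
- Grid B, N = 24 (4 per level): 0.62 SD, against 2.353/2 = 1.18 SD for the mean of 4.
- All four grids: 0.48-0.64 SD at N = 24 and 0.32-0.43 SD at N = 50. Part of the gain at N = 50, and on grid D, comes from having more patients at 1000 mg/day, so grids A and B at N = 24 are the fairer comparison.

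A concentration model works on the same principle, with up to four matched post-dose pairs per patient.

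**Step 5: which pairs match.** Escalation ECG and PK times coincide at predose on Day 1 and at 2 h and 4 h on Days 1 and 15. The 6 h ECG has no PK sample (next sample at 7 h twice daily, 8 h once daily). Extension PK on Day 15 is at predose, 1, 2, 4 and 6 h, but the ECG is tied to none of these.

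**The case against.** The strongest reply is that the trial holds far more data at 1000 mg/day than one escalation cohort. About 70 extension patients take that dose and have a Day 15 ECG, and Section 24.1 makes every treated patient evaluable for safety. A reader might infer that the trial cannot say what QTc does at 1000 mg/day. That inference fails. What remains is narrower: these ECGs are single and untimed, they use a screening baseline, and an analysis described in terms of averaged triplicates does not say how they enter.

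Second, the plan never says that doses will be pooled. It is silent, it also promises patient listings and categorical QTc summaries, and Section 24.5 permits an analysis of variance for dose effects. This is fair, but that clause is optional and is not tied to QT, and the laboratory text shows that dose stratification was written in where it was intended.

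Third, a reader might infer that pooling averages the effect away. It does not: 55-70% remains under the assumed grids. The documents also do not say whether doses above 1000 mg/day were given, so the dilution could be smaller than shown.

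Fourth, Section 6.4.4 reports that in "a serum free hERG study, pexidartinib was shown to bind to the channel", which could be read as a clinical warning. The same section reports no repolarisation effect in Purkinje fibres and no prolongation in the dog study up to its highest dose. The nonclinical record does not establish a QT liability.

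Fifth, regressing predose data limits how far post-dose results could steer the study-specific formula. That is true, but the choice among three corrections is still open. Fixing it now would come after the escalation data were collected, so the choice should rest on the eligibility criterion and all three should be shown.

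Finally, analyses are descriptive in general and the sample size is not based on power. This lowers the priority of the point. It does not remove it, because the bounds are explicitly meant for interpreting the drug's effect on QT.

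**Conclusion.** The point holds for the timed triplicate ECGs. As written, the plan gives either a pooled mean that keeps about 55-70% of the 1000 mg/day effect, or a by-dose mean from about 3-6 patients whose upper bound lies 0.82-1.69 SD above it (8.2-16.9 msec at SD 10). The retained fraction rests on assumed dose grids and a linear effect, and the msec figures on assumed SDs. The SD multiples follow from the cohort size alone.

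The documents do not support saying that QTc at 1000 mg/day is unknowable, that the effect vanishes in the average, or that a QT hazard has been shown. The extension ECGs are a real source at the right dose, whose use the plan leaves undefined. This is an analysis weakness worth correcting, not a flaw that undermines the trial.

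**What to change.** - Name change in QTcF as the single primary QT variable, citing its existing use for eligibility. Report QTcS and QTcB as sensitivity analyses.
- Present the time-point means and one-sided bounds by dose group.
- Add a linear mixed-effects model of change in QTcF on plasma concentration, using the matched 2 h and 4 h escalation pairs from Cycle 1 Days 1 and 15. Take baseline before the first dose of drug, as Section 24.1 defines it. For run-in patients that is the screening ECG, because their Day 1 predose ECG follows a week of treatment. Check linearity and any delay between concentration and effect. Report the predicted change and its one-sided upper 95% bound at the geometric mean Cmax for 1000 mg/day.
- Summarise the extension Day 15 ECGs at 1000 mg/day separately as a sensitivity estimate, stating that they are single recordings without a fixed post-dose hour.

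The cost is analysis time; no new visits or samples are needed. The drawbacks are reliance on a model assumption, no placebo arm to separate drug effect from drift or time of day, and no matched PK sample for the 6 h escalation ECG.
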